2.0 Introduction

2.1 DiseaseOverview

Combined modality therapy with chemotherapy and radiation is a commonly employed treatment approach for patients with various types of HNC [1]. Despite the overall safety and efficacy of this treatment modality, side effects exist, including acute chemoradiation-induced pain, dermatitis, xerostomia, dysgeusia, dysphagia, odynophagia, and oral mucositis. In fact, a majority of patients treated with this modality will experience some degree of oral mucositis (OM) [2]. OM can affect many oral functions including mastication and swallowing which may lead to dehydration, renal failure and necessitate the placement and use of a feeding tube and negatively impact and patient's quality of life (QOL). Severe OM can also predispose a patient to increased risk of infections requiring hospitalization and increased cost of treatment [3]. The severity of these reactions can be so severe that patients who experience treatment-related mucositis are less likely to complete the planned course of therapy without unplanned interruptions in therapy. Previous studies provide evidence that unplanned breaks in radiotherapy for HNC result in worse tumor control [4]. Furthermore, adverse events can increase the cost of healthcare by resulting in preventable hospital admissions for intravenous hydration and nutritional support and procedures including feeding tube placement. In fact, OM has

been shown to be associated with an incremental cost of \$1,700 - \$6,000 per patient, depending on the grade [5].

Despite multiple clinical trials, no single treatment has been proven to be effective in substantially reducing incidence or severity of chemoradiation induced oral mucositis. The current standard practice for the management of OM is symptom management and supportive care with narcotic pain medications and anesthetic mouth rinses and nutritional support with supplementation either by mouth or feeding tube.

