3.2 PatientSelection

InclusionCriteria:

1. Willing and able to understand and sign informed consent form approved by the IRB.
2. Males or females greater than or equal to 18 years old.
3. Biopsy-proven HNC including cancers of the nasopharynx, oropharynx, larynx, hypopharynx, or HNC of unknown primary origin amenable to therapy with radiation and concurrent chemotherapy.
4. Patients who are planned to receive definitive or adjuvant radiotherapy with concurrent platinum-based chemotherapy.
5. Patients whose clinical treatment plans include a continuous course of external beam radiotherapy by intensity-modulated radiation therapy (IMRT) and/or image-guided radiation therapy (IGRT), given as a cumulative dose of 5000 – 7000 cGy in single daily fractions of 180 - 200 cGy, combined with a concurrent course of weekly or tri-weekly cisplatin or carboplatin chemotherapy.
6. Karnofsky performance status score >60.
7. Female patients of child-bearing potential must have a negative pregnancy test prior to enrollment.

ExclusionCriteria:

1. Patient has evidence of current mucositis, mucosal ulceration, or unhealed surgical wounds from surgical resection or biopsy.
2. Prior radiation to the head and neck.
3. Patients with gross tumor involvement of the oral cavity or oral mucosa.
4. Patient planned to receive altered fractionation radiotherapy or multiple fractions per day
5. Patient is using a pre-existing feeding tube for nutritional support at the time of study entry.
6. Women who are pregnant or breast-feeding.
7. Patient plans to receive concurrent chemotherapy, other than the regimens specified in the inclusion criteria.
8. Patients who have chronic immunosuppression or are on current immunosuppressive therapies.
9. Patients who have a contraindication to radiation therapy.
10. Patients enrolled on another investigational trial for oral mucositis prevention.
11. Life expectancy of less than 3 months.
12. Unable or unwilling to adhere to study-specified procedures.

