4.0 Treatment Methods

4.1 Radiation Treatment

Prior to treatment, all patients will provide informed written consent for radiation therapy as per existing institutional policy. All patients will undergo a computed tomography (CT) simulation for treatment planning. Radiation therapy will be delivered with an intensity modulated radiation therapy (IMRT) technique and/or image-guided radiation therapy (IGRT). The prescribed course of radiotherapy will not be altered based on this study. Radiotherapy will be delivered 5 days per week, Monday – Friday with one radiation treatment given per day. The planned cumulative dose of radiation will be determined by the treating physician and will range from 5000 – 7000 cGy in 180 - 200 cGy daily fractions over the course of 5-7 weeks. This treatment is not part of the research protocol.

4.1.1 Definition of Target Volumes:

Target volumes will be outlined per institutional practice and not modified based on this protocol. Target volumes are defined as the following:

Gross Tumor Volume (GTV) represents the region judged to contain gross primary tumor or involved node(s) based on clinical and endoscopic examinations, CT scan, and, when applicable, other imaging techniques.

Clinical Target Volume (CTV) is defined as the GTV plus areas considered at risk for containing microscopic disease delineated by the treating physician. The CTV margins can be narrower when GTV is in the proximity of the spinal cord or critical normal tissues.

Planning Target Volume (PTV) represents an additional margin around the CTV to compensate for the variability of treatment set up and internal organ motion.

4.1.2 Definition of Organs at Risk:

CT-based planning will be used to identify the target volumes and organs at risk (OARs). OARs will be contoured according to the DAHANCA, EORTC, GORTEC, HKNPCSG, NCIC CTG, NCRI, NRG Oncology, and TROG consensus guidelines [24] which are included in table 2 which is provided in appendix 11.4. The dose parameters given to OARs will be recorded (table 3). Dose limits to OARs will be determined by institutional practice and specific dose-constraints will not be required on this protocol. The following radiation doses will be recorded.

Table 3. Dose parameters to OARs to be recorded

Brainstem	Maximum Dose _____
Spinal Cord	Maximum Dose _____
Right Parotid	Mean Dose _____
	V30 _{Gy} _____
Left Parotid	Mean Dose _____
	V30 _{Gy} _____
Parotids (bilateral)	D20 _{cc} _____

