6.0 Statistical Considerations

6.1 Primary Endpoints:

- The incidence of severe (WHO grade 3-4) oral mucositis in patients treated to a cumulative radiation dose of at least 5000 cGy.
- The incidence of severe (CTCAE v. 4.0 grade 3-5) oral mucositis in patients treated to a cumulative radiation dose of at least 5000 cGy.

6.2 Secondary Endpoints:

- Time to onset of severe (CTCAE v. 4.0 grade 3-4) oral mucositis following the initiation of radiotherapy.
- Mean cumulative radiation dose at time of onset of severe (CTCAE v. 4.0 grade 3-4) oral mucositis.
- Duration of oral mucositis.
- The incidence of pain.
- The incidence of dysphagia (CTCAE v. 4.0 and via diet assessment).
- The incidence of xerostomia (CTCAE v. 4.0).
- The incidence of dysgeusia (CTCAE v. 4.0).
- The incidence of trismus (Measurement of interincisal distance).
- The incidence of radiodermatitis (CTCAE v. 4.0).
- Evaluation of OM-related QOL (via FACT-H&N score).
- Incidence of any grade oral mucositis in patients treated to a cumulative radiation dose of at least 5000 cGy.

6.3 Exploratory Endpoints:

- Proportion of patients with severe (CTCAE v. 4.0 grade 3-4) oral mucositis by 5000 and 7000 cGy.
- Proportion of patients with severe (CTCAE v. 4.0 grade 3-4) oral mucositis by schedule of chemotherapy given (weekly versus Q 3 weeks).
- Time to reach planned dose of radiation therapy.
- Amount of narcotic analgesia use during treatment.
- Assessments of breaks in treatment defined as one of the following:
 - Missing at least 1 chemotherapy treatment;
 - Dose reduction in planned cisplatin administration; OR
 - 3 consecutive days of no RT secondary to mucositis. ~
- Proportion of patients who require feeding tube placement during treatment (excluding patients who received a prophylactic feeding tube prior to the initiation of therapy).
- Percent change in body weight during the course of treatment.

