6.5 Analysis

Primary endpoint

If 12 or fewer out of the 45 evaluable severe OM events occur (WHO grade 3-4 or CTCAE v. 4.0 grade 3-5 oral mucositis), we will reject the null hypothesis that the occurrence of severe OM is 0.4 with the addition of LLLT therapy. Point and 90% confidence intervals (using Wilson's method) will also be estimated to describe the primary endpoint.

Secondary endpoints

Descriptive statistics (point and exact 90% confidence interval estimates from the resultant Kaplan-Meier curve) will be generated for the time-to-severe OM and duration of severe OM endpoints. Point and 90% confidence intervals (using Wilson's method) will also be estimated to describe the binary endpoints. Continuous endpoints will be described by 90% confidence intervals using the t-distribution.

Exploratory endpoints

Similar descriptive analyses as described in the above paragraph will be used for the binary, time-to-event and continuous endpoints.

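### Does the exploratory proportion with severe mucositis by 5000 and 7000 cGy need a stated denominator?

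*Combined protocol and SAP*

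**What the plan says.** Section 6.3 includes among the exploratory endpoints "Proportion of patients with severe (CTCAE v. 4.0 grade 3-4) oral mucositis by 5000 and 7000 cGy". The next item there reports severe "oral mucositis by schedule of chemotherapy given (weekly versus Q 3 weeks"), where the word 'by' introduces subgroups.

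Section 6.1 does name a population for the CTCAE primary endpoint: "The incidence of severe (CTCAE v. 4.0 grade 3-5) oral mucositis in patients treated to a cumulative radiation dose of at least 5000 cGy". The WHO primary endpoint and the any-grade endpoint in Section 6.2 carry the same dose restriction.

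Planned dose has a ceiling. Eligibility in Section 3.2 requires radiotherapy "given as a cumulative dose of 5000 – 7000 cGy in single daily fractions of 180 - 200 cGy", and Section 4.1 says that the dose "will range from 5000 – 7000 cGy in 180 - 200 cGy daily fractions".

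For analysis, Section 6.5 gives binary secondary endpoints a point estimate and a 90% Wilson interval, then says of the exploratory endpoints: "Similar descriptive analyses as described in the above paragraph will be used for the binary, time-to-event and continuous endpoints". Section 6.2 also lists a related secondary endpoint, "Mean cumulative radiation dose at time of onset of severe (CTCAE v. 4.0 grade 3-4) oral mucositis".

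**The concern.** A proportion needs a denominator, and this one can be read in three ways.

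- **(a) All evaluable patients.** The numerator is patients whose severe mucositis began at or below the stated dose.
- **(b) Only patients who received that dose.** At 7000 cGy this means patients treated to the exact ceiling.
- **(c) Dose groups.** If 'by' is used as in the chemotherapy-schedule item, the endpoint compares a 5000 cGy group with a 7000 cGy group, and patients in between belong to neither.

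Because 7000 cGy is the planned maximum, the readings diverge there. Under (a) the figure is almost the primary result again, and a reader might take it for separate evidence. Under (b) the sample shrinks, and it could lose patients who stopped early because of mucositis. If the choice is left open, it could be made after the data are seen.

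**Working it through.** **1. The plan's own figure.** Inputs from Sections 6.4 and 6.5: n = 45, null rate 0.40, alternative 0.20, success if 12 or fewer events. With X the number of severe events, P(X ≤ 12 | 45, 0.40) = 0.0446 and P(X ≤ 12 | 45, 0.20) = 0.9005. The stated 5% error and 90% power reproduce, and nothing in Section 6.3 enters this calculation.

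**2. The ceiling.** At 200 cGy per fraction, 35 × 200 = 7000. At 180 cGy, 38 × 180 = 6840 and 39 × 180 = 7020. A patient treated only with 180 cGy fractions cannot land on 7000 within the planned range. Reading (b) at 7000 cGy would exclude all such patients and everyone prescribed less.

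**3. Size of the difference.** The prescription mix and the timing of onset are not in the documents, so the counts here are assumptions: 45 patients, all treated to at least 5000 cGy; 9 severe events (the 20% alternative), of which 6 begin by 5000 cGy and 3 later; no grade 5 event and no first onset after the last fraction.

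The Wilson 90% interval is [p + z²/(2n) ± z√(p(1−p)/n + z²/(4n²))] / (1 + z²/n), with z = 1.645. For 9/45, z²/n = 2.706/45 = 0.0601. The centre is (0.2000 + 0.0301)/1.0601 = 0.217, the half-width is 1.645 × √(0.003556 + 0.000334)/1.0601 = 0.097, and the interval is 12.0% to 31.4%.

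| Reading | Dose | x/n | Estimate | 90% Wilson |
|---|---|---|---|---|
| (a) | 5000 cGy | 6/45 | 13.3% | 7.1% to 23.8% |
| (a) | 7000 cGy | 9/45 | 20.0% | 12.0% to 31.4% |
| (b), 22 reach 7000 | 7000 cGy | 4/22 | 18.2% | 8.4% to 34.9% |
| (b), 11 reach 7000 | 7000 cGy | 2/11 | 18.2% | 6.2% to 42.7% |

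At 5000 cGy, readings (a) and (b) coincide here, because every patient in the set has received that dose. At 7000 cGy, with similar event rates in both groups, they differ mainly in interval width. If the 9 events fell unevenly, reading (b) could range from 0/20 to 9/20 (0% to 45%) with 20 patients at 7000 cGy, so the readings are not interchangeable.

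**4. Which reading the text supports.** Where the authors restrict by dose received, they write the restriction out, as they do three times in Sections 6.1 and 6.2. It is absent here, so (b) adds a condition the item does not contain. Reading (c) has some support from the neighbouring item, but it would compare only patients at the two exact ends of a range in which intermediate doses are allowed. Cumulative occurrence by a dose is the natural meaning.

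**5. Near-repetition of the primary rate.** Under (a), the 7000 cGy figure departs from the CTCAE primary rate only through grade 5 events, patients treated to less than 5000 cGy if they are included, and onset after the last fraction if that is not counted. The overlap is not an error. The pair still adds something: in the illustration, 20.0% − 13.3% = 6.7 points, or 3/45, is onset after 5000 cGy, which the primary rate does not show.

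**6. Dose at onset.** A dose at onset exists only for patients who have an onset, so the Section 6.2 mean can be taken only over them. After the last fraction, cumulative dose is the total delivered. The form in Appendix 11.2 has a radiation dose field and a follow-up assessment type, so any reading can be computed from data already collected.

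**The case for a change.** The best case for a change is that one sentence would close the gap, that other items in Section 6 name their population, and that an open denominator can be chosen after seeing results. The omission is real, and so is the near-repetition at 7000 cGy. Whether the set is the 50 enrolled, the 45 compliant or those treated to at least 5000 cGy is also unstated for this item, though that question concerns Section 6 as a whole. Whether onset after the last fraction counts is likewise unstated, although on cumulative dose it would naturally be counted.

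Three stronger arguments do not stand.

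- **No method is given.** Section 6.5 gives binary endpoints a Wilson interval and extends that to the exploratory endpoints.
- **Reading (a) is biased low.** This holds only if the target is the incidence had everyone received 7000 cGy, which the plan does not state. The size then depends on the assumed mix. Take 20% by 70 Gy, Weibull onset with shape 4, and three quarters of patients at a lower dose. If that dose is 60 Gy, F(60) = 11.4%, the mean is 0.25 × 20 + 0.75 × 11.4 = 13.5%, and the shortfall is 6.5 points. If it is 50 Gy, F(50) = 5.6%, the mean is 9.2%, and the shortfall is 10.8 points. With early onset it can be nil. As a description of the patients treated, reading (a) has no such bias.
- **Severe mucositis will remove patients from reading (b).** Section 2.1 says that "patients who experience treatment-related mucositis are less likely to complete the planned course of therapy without unplanned interruptions in therapy". That concerns interruptions, and does not show that patients fail to reach the planned dose.

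A Kaplan-Meier curve on the dose axis is the one concrete alternative method. In simulation (4,000 trials in each of 12 settings, n = 45, target 20% by 70 Gy, other patients at 60 Gy), its root-mean-square error was 5.9 to 9.3 points, against 5.8 to 8.3 for the simple proportion, and it was never lower in the same setting. It would bring no gain in accuracy.

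**Conclusion.** No change to the plan. This is missing detail in a descriptive exploratory item that an analyst fills sensibly: cumulative occurrence by each dose among the evaluable patients, reported as x/n with the Wilson interval already specified. The primary test, the sample size and the 12-of-45 rule are untouched. Under the illustrative assumptions, the estimate at 7000 cGy is 20.0% on the ordinary reading and 18.2% on the restricted one, the latter with a wider interval. The gap could be larger if events cluster by prescription, but the x/n would show which denominator was used. The conclusion rests on the endpoint remaining untested and exploratory, and on the ordinary reading of its wording.

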1.2 SecondaryObjectives

1. To establish the time to onset of severe oral mucositis following the initiation of radiotherapy with LLLT.
2. To determine the incidence of pain, dysphagia, xerostomia, dysgeusia, trismus, radiodermatitis, and OM-related QOL (via FACT-H&N score) with LLLT.
3. To evaluate the mean cumulative radiation dose at time of onset of severe oral mucositis with LLLT.
4. Determine the duration of oral mucositis.
5. Record the amount of narcotic analgesia use during treatment.
6. Evaluate the number of breaks in chemoradiotherapy with LLLT use.
7. Determine the proportion of patients who require feeding tube placement during treatment.

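### The exploratory treatment-break endpoint counts dose reductions for cisplatin only, so a carboplatin patient whose sole event is a dose reduction is recorded as having no break

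*Combined protocol and SAP*

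**What the plan says.** Section 6.3 introduces the endpoint with "Assessments of breaks in treatment defined as one of the following" and lists three events:

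1. "Missing at least 1 chemotherapy treatment"
2. "Dose reduction in planned cisplatin administration; OR"
3. "3 consecutive days of no RT secondary to mucositis"

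On eligible chemotherapy, inclusion criterion 4 in section 3.2 speaks of the class: "Patients who are planned to receive definitive or adjuvant radiotherapy with concurrent platinum-based chemotherapy". Criterion 5 names the drugs: radiotherapy is to be "combined with a concurrent course of weekly or tri-weekly cisplatin or carboplatin chemotherapy". Section 4.2 leaves the chemotherapy course to the managing medical oncologist and has its frequency and dose recorded for each patient.

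The endpoint serves objective 6 in section 1.2: "Evaluate the number of breaks in chemoradiotherapy with LLLT use". Although section 1.2 lists this as a secondary objective, section 6.3 classes the endpoint as exploratory, and section 6.5 gives exploratory endpoints descriptive analysis only.

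**The concern.** Two of the three events apply whichever drug the patient receives. The middle one does not, yet the eligibility criteria treat cisplatin and carboplatin as equally acceptable. No section extends the dose-reduction event to carboplatin or explains why it stops at cisplatin.

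What is at stake is whether the endpoint measures its own objective. The misclassification runs one way: a carboplatin patient can be wrongly recorded as free of breaks, but the wording cannot create a false break. The Wilson interval planned in section 6.5 for binary endpoints would not reveal the problem, because it reflects sampling error and not misclassification. There is also a practical risk. Two institutions run the same protocol separately, and staff could read the word cisplatin literally at one and loosely at the other.

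**Working it through.** **The plan's own figures.** The documents state no expected break rate, so there is none to reproduce. The only design figures are those for the primary endpoint in sections 6.4 and 6.5. With 45 patients and rejection at 12 or fewer severe events, the exact binomial calculation gives a one-sided type I error of 0.0446 at a true rate of 0.40 and power of 0.9005 at 0.20. The stated 90% power therefore reproduces, and so does the enrolment of 50, as 45/(1 - 0.10) = 50. The break definition enters none of these.

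**Which patients are classified differently.** I read the endpoint as yes or no per patient: a break is present if any listed event occurs. Three events, each present or absent, give 2 x 2 x 2 = 8 histories.

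| Missed chemotherapy | Dose reduced | Three-day RT gap from mucositis | Cisplatin patient | Carboplatin patient |
|---|---|---|---|---|
| no | no | no | no break | no break |
| no | **yes** | no | **break** | **no break** |
| yes | no | no | break | break |
| no | no | yes | break | break |
| yes | yes | no | break | break |
| yes | no | yes | break | break |
| no | yes | yes | break | break |
| yes | yes | yes | break | break |

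The drug changes the answer in one row of eight, the isolated dose reduction. The other two events do not rescue that row, because a reduced dose is neither a missed treatment nor an interruption of radiotherapy.

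**Illustration of size.** Inputs:

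- N = 50, total enrolment (section 6.4).
- c = share of patients on carboplatin. Not in the documents; assumed 10-50%.
- r = proportion of carboplatin patients whose only event is a dose reduction. Not in the documents; assumed 10-30%.

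Missed patients = N x c x r. Understatement of the break rate in percentage points = 100 x c x r.

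| c | r = 10% | r = 20% | r = 30% |
|---|---|---|---|
| 10% | 0.5 (1 point) | 1.0 (2 points) | 1.5 (3 points) |
| 20% | 1.0 (2 points) | 2.0 (4 points) | 3.0 (6 points) |
| 30% | 1.5 (3 points) | 3.0 (6 points) | 4.5 (9 points) |
| 50% | 2.5 (5 points) | 5.0 (10 points) | 7.5 (15 points) |

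For example, 50 x 0.10 x 0.10 = 0.5 and 50 x 0.50 x 0.30 = 7.5. If either c or r is zero, nothing is missed.

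**The case against.** The strongest reply is that this hardly matters. The endpoint is exploratory and described without a test, threshold or stated historical comparator for breaks. The trial has one arm, so no treatment contrast can be biased. Carboplatin doses are recorded anyway, so reductions could be reported beside the endpoint as defined. All of this stands, and it sets the priority of the point. It does not make the rule right: followed as written, it still gives different answers for the same event.

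Three stronger readings are tempting, and the documents support none of them.

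- A reader might infer that every carboplatin patient with a reduced dose is recorded as break-free. That is too broad. Such a patient is still counted if a chemotherapy treatment was also missed or radiotherapy stopped for three days because of mucositis.
- A reader might infer that comparisons between the two centres are distorted. None is planned. Sections 3.1 and 6.4 combine the data for one analysis and section 9.2 plans one joint report. The only chemotherapy subgroup in section 6.3 is by schedule, and it concerns severe mucositis, not breaks. Nothing shows that carboplatin use differs between centres.
- A reader might want one figure for the undercount. The documents supply neither the carboplatin share nor a reduction rate, so any such figure comes from its assumptions.

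**Conclusion.** The mismatch is real, and its effect is narrow. The dose-reduction event in section 6.3 covers one of the two drugs admitted by section 3.2, so a carboplatin patient with an isolated dose reduction is misclassified and the pooled break rate may be understated. The direction is certain. The size is not: it may be zero, and the range of about 0.5 to 7.5 patients of 50 (1 to 15 percentage points) holds only under the assumed shares and reduction rates. It also rests on reading the endpoint as one yes-or-no result per patient. The conclusions on severe mucositis, the 12-of-45 rule, the sample size and the power do not depend on it. This is a minor correction, worth making because it is cheap and removes a known one-directional error.

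**What to change.** In section 6.3, replace the second event with: *Dose reduction in planned platinum (cisplatin or carboplatin) administration*. Leave the other two events as they are, since they already apply to both drugs.

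No new data are needed; the doses recorded under section 4.2 are enough to apply the criterion to every patient. The cost is a few words and, because section 9.1 asks for a reviewed and approved written amendment for any change that is not administrative, a short amendment that can be bundled with another. It should be in place at both institutions before analysis, so that the reading is not chosen after the data are seen. The change concerns only how recorded events are classified. It says nothing about which drug or dose a patient should receive.
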